### **8.2.2 Immunogenicity Data**

Missing immunogenicity values are considered ‘missing completely at random (MCAR)’ and therefore will not contain information that impact the result of the analysis (i.e., not informative). Imputation methods will therefore not be used. The primary objective of lot-to-lot consistency will be analyzed using the PPS and the other primary objective will be analyzed using the PPS, and repeated with the FAS if the numbers of subjects between PPS and FAS differ by >5%.

### **8.2.3 Efficacy Data**

Not applicable.

### **8.3 Multicenter Studies**

Vaccine group effects will be investigated first using a linear model which allows for center differences, but does not consider vaccine-by-center interaction, i.e., the model only considers effects for center and vaccine. A center effect will be included in all analyses of the primary and secondary objectives.

If the statistical model does not converge due to the factor “center”, a model without center effect will be fitted instead.

### **8.4 Multiple Comparisons and Multiplicity**

For lot-to-lot consistency in the statistical analysis of the primary objectives, a combined equivalence hypothesis will be tested.

There is no need for adjustment for multiplicity.

### **8.5 Immunogenicity Subsets**

Not applicable.

### **8.6 Subgroups**

Subgroup analysis will not be applied to the primary objective of lot-to-lot consistency. Using the FAS and PPS, analyses of other primary objectives will be repeated and stratified by

- Baseline HI titer (<1:10 vs. ≥1:10)
- With and without seasonal influenza vaccine in the last 12 months
- Sex (Male vs. Female)

- Race (American Indian or Alaska Native, Asian, Black or African American, Native Hawaiian or other Pacific Islander, White, Other)
- Ethnicity (Hispanic or Latino, Not Hispanic or Latino, Not Reported, Unknown)
- Age per CBER (18 to <65 vs. ≥65 years)
- Age per CHMP (18 to <60 vs. ≥60 years)
- Age (18 – 49, 50 – 64, 65 – 74, ≥75 years)
- Center (as applicable)

For details regarding the analyses by center please see [section 8.3](#) above. Analyses by center will be presented in [Appendix 16.1.9 of the CSR](#).

Analyses of safety data will be repeated and stratified by each of the following: age per CBER (18 to <65 vs. ≥65 years) and age per CHMP (18 to <60 vs. ≥60 years), sex and race for Solicited and Unsolicited AEs. The additional age group (18 - <50, 50 - <65, 65 - <70, and ≥70 years) will be applied to the Solicited AEs. Stratification by age per CBER (18 to <65 vs. ≥65 years) and age per CHMP (18 to <60 vs. ≥60 years) will only be applied to the SAE, NOCD, AESI, AEs leading to death, premature termination, and dose modification.

## 8.7 Derived and Computed Variables

### Demographics

**Age** will be calculated in years using the following formula:

$$\text{Age (years)} = (\text{Date of Visit 1} - \text{Date of Birth} + 1) / 365.25, \text{ round to smallest integer}$$

**Body Mass Index (BMI, kg/m^2)** will be calculated using the following formula:

$$\text{BMI} = \text{Weight (kg)} / \text{Height}^2 (\text{m}^2)$$

### Immunogenicity

Values below the limit of quantification (recorded as “< LQ”) will be set to half that limit (LQ/2).

**Titer greater or equal to a given threshold** is defined as binary variable for non-missing values as:

= 1, if the titer is superior or equal to the given threshold

= 0, otherwise

HI antibody titer  $\geq 1:40$  is defined as binary variable for subjects with non-missing values as:

= 1, if achieving a HI antibody titer  $\geq 1:40$

= 0, otherwise

**Seroconversion** is defined as binary variable for subjects with non-missing values pre-vaccination and post-vaccination as:

= 1, if there is a post-vaccination titer  $\geq 1:40$  for pre-vaccination titer  $< 1:10$

= 1, if there is 4-fold increase (post-vaccination) from pre-vaccination titer  $\geq 1:10$

= 0, otherwise

### Geometric Mean Titer/Concentration

The GMT will be calculated using the following formula:

$$10^{\left\{ \frac{\sum_{i=1}^n \log_{10}(t_i)}{n} \right\}}$$

where  $t_1, t_2, \dots, t_n$  are  $n$  observed immunogenicity titers/concentrations.

### Geometric Mean Ratio

Geometric mean ratios (GMRs) measure the changes in immunogenicity titers/concentrations *within* subjects.

The GMR will be calculated using the following formula:

$$10^{\left\{ \frac{\sum_{i=1}^n \log_{10}\left(\frac{v_{ij}}{v_{ik}}\right)}{n} \right\}} = 10^{\left\{ \frac{\sum_{i=1}^n \log_{10}(v_{ij}) - \log_{10}(v_{ik})}{n} \right\}}$$

where, for  $n$  subjects,  $v_{ij}$  and  $v_{ik}$  are observed immunogenicity titers/concentrations for subject  $i$  at time-points  $j$  and  $k$ ,  $j \neq k$ .

### Duration in the Study

**Duration in the study** is defined in days as:

Last visit date (visit 13)a – Enrollment date (visit 1) + 1

aor premature discontinuation date (in case of withdrawal from the study)

The duration is missing if one of the dates is missing or incomplete.

### Solicited Adverse Events

For details see [section 13.2](#).

### Unsolicited Adverse Events

All adverse events will be characterized according to the date of occurrence related to the vaccination phase as follows:

- **Emergence before vaccination phase:** start date before the first date of injection of study vaccine.
- **Emergence during vaccination phase:** start date on or after the first date of injection of study vaccine or, adverse event increase in severity including to “serious” adverse event.

If the start date is equal to the first date of injection then a “timing” variable (“On injection day, before injection”/“On injection day, after injection”) will be used to define whether the adverse event occurred before or after the injection.

If there are several vaccinations, the adverse event will be associated with the most recent vaccination.

If an adverse event start date is missing or unknown, the adverse event will be considered as emergent.

When start and/or end dates of an adverse event are only partially known, adverse events will be categorized as emergent before, during, or after vaccination phase using the following rules:

- If the partial end date is before (<) the first study vaccination (i.e., year or year & month is/are before the first study vaccination year or year & month) then the adverse event is emergent before vaccination phase.
- If the partial start date is equal or after (≥) the first study vaccination (i.e., year or year & month is/are after or the same as the first study injection year or year & month) then the adverse event is emergent during vaccination phase.

The **maximum event severity** is the greatest severity associated with a preferred term for a reported adverse event according to the following order: Mild < Moderate < Severe. Unknown/ Missing severity is considered as severe (except for the definition of emergence).

Multiple AEs with the same PT for the same subject are counted only once.

**Vaccination-related Adverse Events** are those for which the cause has been evaluated by the investigator, and recorded either as possibly related, probably related or unknown/missing.

#### Safety Laboratory Data

Not applicable

#### Pre-study, Concomitant and Post-Study Medications

A **pre-study medication** is a medication used only before the first study vaccination (i.e. medication end date < first study vaccination date).

A **post-study medication** is a medication used only after study termination (i.e. medication start date > study termination date). This will not be collected in the clinical database and will not be reported in the CSR.

All other medications are **concomitant**.

When start and/or end dates of a medication intake are missing, the medication is considered as concomitant with the study vaccination schedule.

If the first study vaccination date is missing then the medication is considered as concomitant with the study vaccination schedule, provided that the study vaccine was administered to the subject.

### **8.8 Analysis Software**

All analyses will be performed using SAS® Software version 9.1 or higher.

### **8.9 Data Transformation**

Distributions of antibodies are generally skewed to the right (Nauta, 2010). Therefore, prior to any statistical analysis that assumes normally distributed observations, antibody titers or concentrations will be log10-transformed. GMTs and their 95% CIs are computed by exponentiating (base 10) the least squares means and 95% CIs of the log10 titers (obtained from a fitted model as appropriate).

## **9. STUDY SUBJECTS**

### **9.1 Disposition of Subjects and Withdrawals**

All subjects who provide informed consent will be accounted for in this study. The frequencies and percentages of subjects in each analysis set, study withdrawals, subgroups, and major protocol deviations will also be presented.

The time the subjects are under observation will be summarized by vaccine and overall using summary statistics (mean, standard deviation (SD), minimum, median, maximum).

## **10. DEMOGRAPHICS AND OTHER BASELINE CHARACTERISTICS**

### **10.1 Demographics**

Age, height, weight, body mass index will be summarized by reporting the mean, standard deviation, median and range, and will be calculated by vaccine lot/group and overall.

The frequencies and percentages of subjects by sex, ethnic origin, race, and previous influenza vaccination (in the past 12 months) will be presented by vaccine lot/group and overall. Demographic data will be tabulated for the All Enrolled, PPS, and Overall Safety Set. If the percentage of subjects excluded from the PPS is greater than 5%, the demographic data will be tabulated for the FAS as well.

### **10.2 Medical History**

The frequencies and percentages of subjects with medical history will be presented by MedDRA system organ class and preferred term, by vaccine lot/group and overall. Medical history data will be tabulated for the All Enrolled, PPS, and Overall Safety Set. If the percentage of subjects excluded from the PPS is greater than 5%, the medical history data will be tabulated for the FAS as well.

## 11. IMMUNOGENICITY ANALYSIS

### 11.1 Blood Samples

The frequencies and percentages of subjects with blood draws will be summarized overall and by vaccine group. Data will be tabulated for the All Enrolled set.

### 11.2 Primary Objectives Analysis

For lot-to-lot consistency, the following equivalence hypotheses will be tested simultaneously:

$$H_0: (\mu_{\text{lot A}} - \mu_{\text{lot B}}) \leq -0.176 \text{ or } (\mu_{\text{lot A}} - \mu_{\text{lot B}}) \geq 0.176 \text{ or}$$

$$(\mu_{\text{lot A}} - \mu_{\text{lot C}}) \leq -0.176 \text{ or } (\mu_{\text{lot A}} - \mu_{\text{lot C}}) \geq 0.176 \text{ or}$$

$$(\mu_{\text{lot B}} - \mu_{\text{lot C}}) \leq -0.176 \text{ or } (\mu_{\text{lot B}} - \mu_{\text{lot C}}) \geq 0.176$$

vs.

$$H_1: (\mu_{\text{lot A}} - \mu_{\text{lot B}}) > -0.176 \text{ and } (\mu_{\text{lot A}} - \mu_{\text{lot B}}) < 0.176 \text{ and}$$

$$(\mu_{\text{lot A}} - \mu_{\text{lot C}}) > -0.176 \text{ and } (\mu_{\text{lot A}} - \mu_{\text{lot C}}) < 0.176 \text{ and}$$

$$(\mu_{\text{lot B}} - \mu_{\text{lot C}}) > -0.176 \text{ and } (\mu_{\text{lot B}} - \mu_{\text{lot C}}) < 0.176$$

Here,  $H_1$  refers to the alternative hypothesis of pairwise equivalence (consistency) transformed to the log10 scale. Accordingly,  $\mu_{\text{lot A}}$ ,  $\mu_{\text{lot B}}$ , and  $\mu_{\text{lot C}}$  denote the means of log10-transformed Day 43 titers of the corresponding lot groups. The lot-to-lot consistency will be claimed if the two-sided 95% CIs of all the three pairwise comparisons are within the equivalence ranges. Significance level to all these tests is  $\alpha = 5\%$ , which needs no adjustment for multiplicity as all hypotheses have to be rejected (union-intersection principle).

The primary analysis population for testing the null hypotheses above will be the Per Protocol Set (PPS). If the percentage of subjects excluded from the PPS for analysis of immunogenicity is greater than 5%, a supporting analysis based on the FAS will be performed to compliment the analysis based on the PPS.

For evaluating immune responses to aH5N1 vaccine (percentage of subjects with HI titer  $\geq 1:40$ ) according to CBER criteria:

- The lower bound of the adjusted 2-sided 95% CI for the percentage of subjects achieving an HI antibody titer  $\geq 1:40$  should meet or exceed 70% and 60% respectively for the two different age cohorts (18 to <65 years of age and  $\geq 65$  years of age), the following hypothesis will be tested:

$$H_0: (\pi_i - \pi_0) \leq 0 \quad \text{vs.} \quad H_1: (\pi_i - \pi_0) > 0$$

To assess CBER criteria, summarize [Table 11-1](#) below, the lower limit of the 95% CI of the two endpoints (proportion of Subjects with HI titer  $\geq 1:40$  and proportions of subjects achieving seroconversion) will be compared with the pre-specified thresholds, in the two age cohorts (18-64,  $\geq 65$  years). Similarly, CHMP criteria will be assessed.

**Table 11-1: Comparison of CHMP and CBER Criteria for Evaluation of Influenza Vaccines**

CHMP Criteria	Adults 18 – <60 Years	Adults <math>\geq 60</math> Years
Percentage of subjects with HI antibody titer $\geq 1:40$	> 70%	> 60%
Geometric Mean Ratio	> 2.5	> 2.0
Percentage of subjects with Seroconversion a	> 40%	> 30%
CBER Criteria	Adults 18-64 Years	Adults <math>\geq 65</math> Years
Lower limit of the two-sided 95% CI for percentage of subjects with HI antibody titer $\geq 1:40$	$\geq 70\%$	$\geq 60\%$
Lower limit of the two-sided 95% CI for percentage of subjects with Seroconversion a	$\geq 40\%$	$\geq 30\%$

a Seroconversion = either a pre-vaccination (baseline) HI titer  $< 1:10$  and post-vaccination HI titer  $\geq 1:40$ , or a pre-vaccination HI titer  $\geq 1:10$  and a  $\geq 4$ -fold increase in post-vaccination HI antibody titer

In addition, results collected at Day 22 will also be evaluated against the CBER criteria for both age cohorts. Results collected at Day 22 will also be evaluated against the CHMP criteria.

The analysis will be based on the PPS. If the percentage of subjects excluded from the PPS for analysis of immunogenicity is greater than 5%, a supporting analysis based on the FAS will be performed to compliment the analysis based on the PPS.

#### **11.4 Exploratory Objectives Analysis**

Not applicable.

**12. EFFICACY ANALYSIS**

**12.1 Primary Objectives Analysis**

Not applicable.

**12.2 Secondary Objectives Analysis**

Not applicable.

**12.3 Exploratory Objectives Analysis**

Not applicable.

## 13. SAFETY ANALYSIS

The analysis of safety assessments in this study will include summaries of the following categories of safety data collected for each subject:

- Vaccine exposure.
- Solicited local and systemic adverse events.
- Unsolicited adverse events.

### 13.1 Analysis of Extent of Exposure

The frequencies and percentages of subjects with vaccinations will be summarized overall and by vaccine group. Data will be tabulated for the All Enrolled Set.

#### 13.1.1 Safety Completeness Analysis

##### Solicited adverse events

The safety completeness analysis on solicited adverse events aims to identify subjects who completed diary cards, irrespective of severity. The analysis will show the number of subjects with *valid data* by solicited adverse event and time point. *Valid data* in the context of the safety completeness analysis are all data entered in the diary card (including implausible values) except “Not done/unknown”.

Four summaries will be produced:

- The frequencies of subjects who provide diary cards by vaccine group and collection method.
- For each solicited adverse event, the frequencies of subjects with valid data will be presented by vaccine group and timepoint: 30 min, Day 1-3 (with and without the 30-minute interval), Day 4-7, and Day 1-7 (with and without the 30-minute interval).
- For each type of solicited adverse event (local, systemic) and indicators of solicited adverse events, such as analgesic use the frequencies of subjects with valid data by vaccine group, aggregated over time points: 30 min, Day 1-3 (with and without the 30-minute interval), Day 4-7, and Day 1-7 (with and without the 30-minute interval).
- For each solicited adverse event, the frequencies of subjects with valid data by vaccine group, aggregated over time points: 30 min, Day 1-3 (with and without the 30-minute interval), Day 4-7, and Day 1-7 (with and without the 30-minute interval).

For the corresponding percentages, the denominator will be the respective numbers of exposed subjects, i.e., subjects who received a vaccination and were still in-study for that time point or time interval, irrespective of whether a diary card was present or not.

All analyses will be based on the ‘as treated’ analysis set.

### **13.2 Solicited Local and Systemic Adverse Events**

Only solicited local and systemic adverse events reported in the diary card will be analyzed. Implausible measurements will not be taken into consideration in the analysis but listed in the Appendix of the CSR (see [section 6.3](#) of this document).

Solicited adverse events will be collected at 30 minutes, Day 1 (after 30 minutes) and then daily until Day 7 using structured diaries. The analyses of solicited adverse events will be done separately for 30 minutes and based on the intervals: Day 1-3 (with and without the 30-minute interval), Day 4-7, and Day 1-7 (with and without the 30-minute interval). In addition solicited adverse events ongoing after Day 7 will be presented as unsolicited AE.

For erythema, induration, and ecchymosis recorded originally as diameters (mm), the following categorization will be used to summarize the data:

Grade 0 (<25 mm), any (25-50 mm [Grade I], 51-100 mm [Grade II], >100 mm [Grade III]).

Injection site pain and systemic AEs (except fever) occurring for the 7 days including each vaccination will be summarized according to “mild”, “moderate” or “severe”.

Each solicited local and systemic AE will also be further summarized as “none” versus “any”.

Body temperature will be broken down by route of measurement according to the recommendations of the Brighton collaboration and will be summarized according to the 2 schemes described below:

- by 0.5 °C increments: <36.0, ≥36.0-<36.5, ≥36.5-<37.0, ≥37.0-<37.5, ≥37.5-<38.0, ≥38.0-<38.5, ≥38.5-<39.0, ≥39.0-<39.5, ≥39.5-<40.0, ≥40.0°C
- <38.0, ≥38.0 °C

Fever, defined as a body temperature of ≥38°C irrespective of route of measurement, will be integrated to the summaries as an indicator of a systemic adverse event.

The analyses will encompass summaries of the data on five levels:

1. Daily reports of subjects with solicited adverse events.
2. Time of first onset of solicited adverse events (excluding 30 min measurement).

3. Solicited adverse events, maximum event severity by event and interval Day 1-3, Day 4-7, and Day 1-7, each without 30 min.
4. Duration of solicited adverse events.
5. Solicited adverse events and indicators of solicited adverse events, occurrence of at least one event by category (local, systemic) and interval Day 1-3, Day 4-7 and Day 1-7, each without 30 min.

For each of the time points or time intervals presented in the summaries, only subjects with at least one plausible observation (i.e., any non-missing values but excluding “Not done/unknown” and implausible values) for the solicited adverse events in the interval of interest will be considered. Subjects without plausible data (i.e. missing values or reported as “Not done/unknown” and implausible values) will be removed from the denominator to prevent a downward bias (towards zero).

#### Level 1: Daily reports of solicited adverse event

For each of the time points only subjects with at least one plausible observation (i.e., any non-missing values but excluding “Not done/unknown” and implausible values) for the solicited adverse event in the interval of interest will be considered. Subjects without plausible data (i.e. missing values or reported as “Not done/unknown” and implausible values) will be removed from the denominator in order to prevent a downward bias (towards zero). Data collected will be summarized (frequencies and percentages of subjects) by vaccine group, solicited adverse event, vaccination number and time point.

#### Level 2: Time of first onset of solicited adverse events

The **time of first onset** is defined, for each subject, for each solicited adverse event, as the time point at which the respective solicited adverse event first occurred. For erythema, induration and ecchymosis the following threshold will be used:  $\geq 25$  mm. The summary will provide the frequencies and percentages of subjects with first onset of each solicited adverse events by vaccine group and by each time point.

**Table 13.2-1: Example for Time to First Onset of Solicited Adverse Events**

Vaccination	Subject Number	Day 1 a	Day 2	Day 3	Day 4	...	Day 7
1	001	None	Severe	Moderate	None	...	None
	002	Mild	None	None	Moderate	...	Missing
	003	Moderate	Mild	None	Severe	...	Mild
	004	Mild	Mild	None	None	...	None
2	001	None	None	None	None	...	Not done
	002	None	Mild	Mild	Missing	...	Missing
	003	Severe	None	Mild	Missing	...	None
	004	Missing	Missing	Missing	Severe	...	Mild

a Exclude 30 minutes after vaccination.

For each vaccination the first onset of the adverse event will be used for each subject. For any vaccination the worst adverse event across all vaccinations per time point will be used. Note, ‘not done’ is treated identical to ‘missing’. A mock-up table is shown in [Table 13.2-2](#) below.

**Table 13.2-2: Time to First Onset of Solicited Adverse Events**

Vaccine group A

Vaccination	Adverse event		Number (%) of Subjects					
			DAY 1 a (N=4)	DAY 2 (N=4)	DAY 3 (N=4)	DAY 4 (N=4)	...	DAY 7 (N=4)
1	XY	n	4	4	4	4	...	3
		ANY	3 (75.0%)	1 (25.0%)	0 (0%)	0 (0%)	...	0 (0%)
		Mild	2 (50.0%)	0 (0%)	0 (0%)	0 (0%)	...	0 (0%)
		Moderate	1 (25.0%)	0 (0%)	0 (0%)	0 (0%)	...	0 (0%)
		Severe	0 (0%)	1 (25.0%)	0 (0%)	0 (0%)	...	0 (0%)
2	XY	n	3	3	3	2	...	2
		ANY	1 (33.3%)	1 (33.3%)	0 (0%)	1 (50.0%)	...	0 (0%)
		Mild	0 (0%)	1 (33.3%)	0 (0%)	0 (0%)	...	0 (0%)
		Moderate	0 (0%)	0 (0%)	0 (0%)	0 (0%)	...	0 (0%)
		Severe	1 (33.3%)	0 (0%)	0 (0%)	1 (50.0%)	...	0 (0%)
ANY	XY	n	4	4	4	4	...	3
		ANY	3 (75.0%)	1 (25.0%)	0 (0%)	0 (0%)	...	0 (0%)
		Mild	2 (50.0%)	0 (0%)	0 (0%)	0 (0%)	...	0 (0%)
		Moderate	0 (0%)	0 (0%)	0 (0%)	0 (0%)	...	0 (0%)
		Severe	1 (25.0%)	1 (25.0%)	0 (0%)	0 (0%)	...	0 (0%)

N: no. of subjects with data at a time point across all vaccinations.

n: no. of subjects with data at a time point for that specific vaccination.

a Exclude 30 minutes after vaccination.

Level 3: Solicited adverse events, maximum event severity by event and interval

The **maximum event severity** will be defined if there is at least one plausible non-missing observation (excluding “Not done/unknown” and implausible values) within this time interval, Each subject’s data will be aggregated across the time points of the interval and summarized according to the maximal severity observed for each adverse event, followed by a summary across subjects for each vaccine. Subjects without any solicited adverse events in the interval, i.e., missing values at each of the requested time points, will be removed from the denominator.

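### SAP 13.2 Level 2 dates a first onset to the first reported diary day even when earlier days are missing, so the vaccination 2 percentages in Table 13.2-2 cannot be read as an onset distribution (minor)

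*SAP*

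**What the plan says.** SAP 13.2, Level 2, defines time of first onset for each subject and solicited event "as the time point at which the respective solicited adverse event first occurred". The text under Table 13.2-1 adds: "For each vaccination the first onset of the adverse event will be used for each subject". It also says that an entry marked not done is handled as missing. A subject can therefore appear on at most one day per event and vaccination.

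Table 13.2-2 is the mock-up built from the example diaries in Table 13.2-1. Its footnote defines the daily denominator as "n: no. of subjects with data at a time point for that specific vaccination". This follows the general rule in 13.2, under which subjects without plausible data at the time point or interval "will be removed from the denominator to prevent a downward bias (towards zero").

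Level 2 has no rule for a first report that follows missing days.

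**The concern.** A first-onset table is naturally read as showing what share of subjects started the event on each day. Two features of Level 2 work against that reading.

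- **Onset day.** If the earlier diary days are blank, the first reported day is only the latest possible onset day. The mock-up nevertheless enters it as the onset day.
- **Denominator.** A subject whose onset is already recorded certainly does not have a first onset on a later day. Dropping that subject because the later day is blank discards known information.

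Gaps are foreseeable. Protocol 3.4.1 requires blank or illegible diary fields to be entered as missing and forbids corrections after the card is delivered. SAP 8.2.1 rules out imputation. The mock-up is the template for programming, so its convention would carry into this table for every solicited event and vaccine group. What is at stake is the apparent timing of reactogenicity: some early onsets would be shown as later ones.

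**Working it through.** **Inputs: vaccination 2 rows of Table 13.2-1 (Days 1, 2, 3, 4, ..., 7)**

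- "001 None None None None ... Not done": no displayed onset.
- "002 None Mild Mild Missing ... Missing": first onset Day 2, mild.
- "003 Severe None Mild Missing ... None": first onset Day 1, severe.
- "004 Missing Missing Missing Severe ... Mild": first report Day 4, severe; Days 1 to 3 unknown.

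**Step 1. Reproduce the SAP's cells.** Percentage = first onsets on the day / subjects with data on the day.

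| | Day 1 | Day 2 | Day 3 | Day 4 | Day 7 |
|---|---|---|---|---|---|
| First onsets | 1 | 1 | 0 | 1 | 0 |
| n with data | 3 | 3 | 3 | 2 | 2 |
| Percentage | 33.3% | 33.3% | 0% | 50.0% | 0% |

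These match the printed any-severity row. The displayed n and any-severity cells of the vaccination 1 and any-vaccination blocks also reproduce.

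**Step 2. Compare with the subjects.** 1/3 + 1/3 + 0/3 + 1/2 + 0/2 = 116.7%. Subjects 002, 003 and 004 have a displayed onset: 3/4 = 75%. In the vaccination 1 and any-vaccination blocks no data are missing on Days 1 to 4; they give 75.0% + 25.0% = 100%, and 4 of 4 subjects have an onset. The discrepancy is confined to vaccination 2.

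**Step 3. Is n a risk set instead?** Subjects with data and no earlier recorded onset number 3, 2, 1 and 2 on Days 1 to 4. The printed n is 3, 3, 3 and 2. It keeps subject 003 on Days 2 and 3 after that subject's onset, so the cells are not daily hazards either.

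**Step 4. Intermittent gaps (assumed figures).** Suppose a share p of subjects have onset on Day 1 lasting into Day 2, a share m of Day 1 entries is blank at random, and Day 2 is complete.

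- SAP rule, Day 1: p(1 − m)/(1 − m) = p.
- SAP rule, Day 2: the redated onsets, pm, against a true value of 0.
- SAP rule, total: p(1 + m).
- One fixed denominator: p(1 − m) + pm = p.

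With p = 60% and m = 10%, the SAP rule gives 54/90 = 60% and 6/100 = 6%, total 66%. The fixed denominator gives 54% + 6% = 60%. For m = 5% or 20% the SAP total is 63% or 72%.

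**Step 5. Diaries that stop (assumed figures).** Take 100 subjects with 10 true Day 4 onsets, and let 20% stop their diary at random after giving some earlier data. The SAP rule gives 8/80 = 10%, which is correct. The fixed denominator gives 8/100 = 8%, which is low.

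**Step 6. Header check.** The footnote defines N as subjects with data at a time point across all vaccinations. On Day 7 subject 002 is missing after both doses, so N is 3. The header prints 4, while the any-vaccination block prints n = 3.

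**The case against.** The strongest reply is that the table contains no arithmetic error in these cells. The denominator is disclosed, n is printed above every percentage, and nothing in the SAP says that the daily figures are to be added. That stands. The 116.7% is not printed anywhere in the SAP; it is a sum across columns with different n, in one block of a four-subject illustration. Because counts and n are shown, a careful reader can recover the shares.

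A reader might also infer that a day with 10% or 20% of entries missing inflates that day's percentage by 1/0.90 = 1.11 or 1/0.80 = 1.25. The documents do not support this as a general statement. Those factors compare with a fixed denominator, not with the truth, and a blank entry can remove an onset from the numerator as well as a subject from n. Under random drop-out the SAP rule is right and the fixed denominator is low (Step 5), which is the downward bias that 13.2 sets out to avoid. The bias comes from redated onsets after gaps, not from a shrinking n alone.

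Nor do the documents show that gaps will differ between vaccine and placebo. SAP 13.1.1 already tabulates valid diary data by vaccine group and time point, so such a difference would be visible.

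Finally, it may be said that the primary safety objective is compromised. It is not. Protocol 7.1.4 defines the solicited safety endpoints as percentages of subjects by interval; SAP Levels 3 and 5 supply those from interval data. What the reply does not answer is subject 004, whose onset is placed on Day 4 with three unknown days before it.

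**Conclusion.** The point holds in a limited form. Level 2 assigns a definite onset day where the diary cannot support one. Its daily percentages are then neither a first-onset distribution nor a hazard. In the example this affects vaccination 2 only: the cells total 116.7% against 75% of subjects with a displayed onset. In the trial, intermittent gaps would overstate later onset days, by an amount that depends on how often early days are blank and how long events last; the figures in Step 4 are assumptions. Random drop-out does not cause this by itself.

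Days 5 and 6 are elided in Table 13.2-1, so 3 of 4 rests on the displayed days. An onset in subject 001 on either day would make it 4 of 4, with the sum still above 100%.

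Severity is minor. One descriptive reactogenicity table is affected; Levels 3 and 5 and all immunogenicity inference are not.

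**What to change.** In SAP 13.2 Level 2 and Table 13.2-2:

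1. Report an onset preceded by a missing day in a separate row, *first reported on Day x, earlier day missing*, and not as a Day x first onset.
2. Choose how the percentages are to be read.
   - As a distribution: also show them on one denominator per vaccination, namely subjects with at least one plausible observation in Day 1 to 7 (the inclusion principle of Level 3). State that this is slightly low when diaries stop early.
   - Otherwise: label the percentages as day-specific and not additive.
3. Correct the Day 7 header N from 4 to 3.

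With the separate row and the single denominator of 4, the vaccination 2 example becomes Day 1 25%, Day 2 25%, Day 3 0%, Day 4 0%, plus 25% in the separate row (subject 004): total 75%, or 3 of 4.

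The cost is a few lines of SAP text and one table shell. No new data are needed.
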